9.3. Analysis of Safety

All safety analyses will be performed on the Safety Analysis Set. All safety data will be listed in individual subject listings by treatment and subject.

For the evaluation of safety parameters, the continuous variables will be summarized descriptively per treatment, period, time point, and overall, by N, arithmetic mean, median, SD, and minimum and maximum values. Categorical variables will be presented in frequency tables with the counts of observations and corresponding percentages.

9.3.1. Adverse Events

Adverse events will be mapped to the Medical Dictionary for Regulatory Activities (MedDRA™) dictionary.

AEs will be assigned to each treatment period as follows:

- **Treatment-emergent AEs in Period 1**
 - All AEs with start date/time on or after the start of dosing in Period 1 and before the start of the washout period (if not missing) having been absent in pre-treatment (or) worsen in severity relative to the pre-treatment state following administration of study drug in Period 1.
 - AEs that emerge during the washout period and/or are causally related to the study treatment administered in the time preceding the washout period.

- **Treatment-emergent AEs in Period 2**
 - All AEs with start date/time on or after the start of dosing in Period 2 having been absent in washout period (or) worsen in severity relative to the pre-treatment state following administration of study drug in Period 2.
 - AEs that emerge during the Follow-up Phase and/or are causally related to the study treatment administered in the time preceding the Follow-up Phase.

AE summaries will be displayed by treatment for:

- **Overall AE Summary**
 - A general summary that includes all TEAEs reported throughout the study, regardless of the treatment period.
- **Period-Specific AE Summaries**
 - Separate TEAE summaries for each treatment period (1 and 2).

The AEs that occur prior to treatment in Period 1 will be summarized in listings and not included in TEAE summary tables. This helps in understanding their impact without confounding the safety profile of the specific treatment periods. All other adverse events will be considered 'pre-treatment'.

In the case where it is not possible to define an AE as being treatment emergent or not, the AE will be classified as treatment emergent as the most conservative approach.

Analyses of AEs will be performed for those events that are considered treatment emergent. The AE tables will include the number and percentage of subjects with at least one AE, the number of AEs by MedDRA primary SOC (sorted in decreasing order of the total frequency) and MedDRA PT (sorted in descending order of the total frequency within each SOC) unless otherwise indicated. A subject with more than one occurrence of the same AE in a particular SOC/PT will be counted only once in the total of those experiencing AEs in that particular SOC /PT.

The AE Relationship to Study Treatment will be combined where Related includes the categories Possibly Related, Probably Related, Definitely Related and Unrelated includes Not Related.

For the overall summary tables and the AE tables summarized by intensity, a subject who has more than one AE within a particular category (SOC or SOC /PT combination) with differing intensities will be counted for each recorded intensity.

An overview table of AEs will be presented by treatment with the number and percentage of subjects with at least one:

- Treatment-emergent AE (TEAE)
- Treatment-related TEAE
- TEAE by severity: mild, moderate, severe
- Serious TEAE
- TEAE leading to study withdrawal
- TEAE leading to death

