7.7.8. Adverse Events and Serious Adverse Events during the Washout and Follow-up Period

If AEs emerge during the washout or Follow-up period, the causal relationship will be assessed in relation to the study treatment administered in the time preceding the washout or Follow-up period.

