2. STUDY DESIGN

This is an open-label, single-center, single-dose, randomized, two-way (two-period) crossover study in healthy volunteers. Each Subject will complete Screening, Baseline, Treatment (two cross-over periods), and Follow-up Phases.

The Screening Phase will be conducted on an outpatient basis between 14 and 3 days prior to the Baseline visit. Subjects will be instructed to maintain a < 2-gram sodium diet and abstain from caffeine-containing products within 2 days prior to admission to the Clinical Research Unit (CRU). On arrival to the CRU (Day 0), baseline and final qualification assessments will be performed.

The Treatment Phase will be comprised of two crossover periods separated by a 3 ± 1 day washout period. During each CRU admission and through the washout period, Subjects will continue a < 2-gram sodium diet and abstain from caffeine-containing products. At baseline (Day 0), subjects will be randomly assigned in a 1:1 ratio to 1 of 2 treatment sequences to receive intravenous (IV) furosemide or subcutaneous (SC) SCP-111 in the abdomen in Crossover Periods (i.e., IV followed by SC or vice versa). Blood samples will be collected to measure furosemide plasma concentrations at pre-dose and for 12 hours post-dose. Prior to dosing in each Treatment Phase, subjects will void their bladder completely and urine will be collected starting after the injection through 12 hours post injection to determine total urine output and urinary sodium and potassium excretion. Assessment of injection site pain will be conducted for IV and SC administration using an 11-point pain scale. Photographs of the injection site will be performed prior to the IV and SC injection (baseline) and 4 hours post IV administration and 6 hours post SC administration. In addition, a photograph will be taken of the IV and SC injection site for any adverse event (AE) (i.e., erythema, edema, pruritus, bruising) that occurs at the site at the time of the event. Subjects will remain domiciled in the CRU for each Treatment Phase through 12 hours after administration of study drug. After final assessments are performed, subjects may be discharged from the CRU if safety parameters are acceptable to the Investigator.

The Follow-up Phase will occur 24-48 hours (Day 5 ± 1) after discharge from the CRU following Crossover Period 2, completing Subjects' study participation.

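### SAP 9.3.1's overlapping adverse-event rules can count a late injection-site reaction under the wrong treatment, or under both

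*SAP*

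**What the plan says.** SAP 2 (Study Design) describes a 1:1 randomised crossover ("i.e., IV followed by SC or vice versa"), with this timing: "The Treatment Phase will be comprised of two crossover periods separated by a 3 ± 1 day washout period". The SC dose goes into the abdomen and the IV dose into a vein.

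SAP 9.3.1 makes the period the unit of assignment ("AEs will be assigned to each treatment period as follows") and then displays the summaries by treatment. In a two-period crossover, the period thus decides the treatment column. The bullets that matter are:

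- Period 1, second bullet: "AEs that emerge during the washout period and/or are causally related to the study treatment administered in the time preceding the washout period".
- Period 2, first bullet: "All AEs with start date/time on or after the start of dosing in Period 2 having been absent in washout period", or events that "worsen in severity relative to the pre-treatment state following administration of study drug in Period 2".
- Period 2, second bullet: "AEs that emerge during the Follow-up Phase and/or are causally related to the study treatment administered in the time preceding the Follow-up Phase".

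Protocol 7.7.8 covers events that emerge in washout or Follow-up: "the causal relationship will be assessed in relation to the study treatment administered in the time preceding the washout or Follow-up period". SAP 9 gives the SAP precedence over the protocol.

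**The concern.** The two treatments are given at different body sites only a few days apart, so the site of a local reaction usually identifies its treatment better than its onset date does. The SAP rule ignores the site, and its bullets overlap with no statement of which one prevails. A local reaction to the first treatment that starts after the second dose can then be reported under the second treatment, or under both.

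Safety and tolerability of SCP-111 is a secondary objective, and Amendment 3 added photographs specifically to evaluate injection-site events. The by-treatment adverse-event table is where a reader would look for local reactions, and with about 20 subjects per treatment a single event is visible in it. These events have known start dates, so the partial-date rules in SAP 4.4 do not help. The default in 9.3.1 for unclear cases settles only whether an event is treatment-emergent, not which treatment it belongs to.

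**Working it through.** **Step 1. Apply the rules to one case.** Subject randomised SC then IV; abdominal-site reaction with recorded start on or after the Period 2 (IV) dose.

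| Causality judgment and reading of and/or | Period 1 (SC) rule met? | Period 2 (IV) rule met? | Column |
|---|---|---|---|
| Not judged related to SC | No | Yes | IV |
| Related to SC, read as 'or' | Yes: no onset limit | Yes | Both |
| Related to SC, read as 'and' | No: onset not in washout | Yes | IV |

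The Period 2 rule takes every event with that onset and has no exception for events attributed to Period 1, so no row ends in SC only. Onset during Follow-up gives the same result through the second Period 2 bullet.

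**Step 2. Neighbouring cases.**
- An SC-site reaction that started before Period 2 dosing belongs to Period 1. If it worsens after the IV dose, the worsening wording can bring it into Period 2 as well.
- In an IV-then-SC subject, an IV-site reaction starting after the SC dose follows the same logic and lands under SC, or under both.

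**Step 3. Exposed window.** Period 2 dosing is 2 to 4 days after Period 1. Discharge is at about 12 h and Follow-up is 24 to 48 h later, so Follow-up is 36 to 60 h after the Period 2 dose. For an SC-site reaction the window runs from 2–4 days after the SC dose to between 3.5 days (2 days + 36 h) and 6.5 days (4 days + 60 h). Only the SC-then-IV sequence is exposed: 10 or 11 of 21 subjects, or 9 of 18.

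**Step 4. Denominators.** The plan enrols 21 so that 18 complete. The figures agree: 18 / (1 − 3/21) = 21. The sample-size calculation is not in dispute here and supplies only the denominators.

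**Step 5. Effect of one event.** Take one true SC-site reaction, N subjects under each treatment, and no other event of the same term in that subject.

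| | SC | IV | SC − IV | Shift from truth |
|---|---|---|---|---|
| Truth | 1/N | 0 | +1/N | – |
| Counted as IV only | 0 | 1/N | −1/N | 2/N |
| Counted in both | 1/N | 1/N | 0 | 1/N |

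- N = 21: 1/21 = 4.8 points. Shift 2/21 = 9.5 points (IV only) or 4.8 points (both).
- N = 18: 1/18 = 5.6 points. Shift 2/18 = 11.1 points (IV only) or 5.6 points (both).

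**The case against.** Several points on the other side are sound and limit the finding.

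- **Onset, not detection.** The SAP goes by recorded start date. A bruise noticed at the Follow-up examination but dated to washout is a Period 1 event. A reader might infer that anything first found at Follow-up goes to IV; the text does not say so.
- **The SC rate is not always lowered.** A reader might infer that late SC reactions simply disappear from the SC column, so that two such events among 20 subjects per treatment would read 0% SC and 10% IV. That needs the 'and' reading or a not-related judgment. Under the 'or' reading the same events give 10% in both columns. The mirror case pushes the other way, so a systematic bias in favour of SC is not established.
- **Protocol 7.7.8 does not name Period 2.** It can be read as pointing to the most recent treatment only, but Protocol 7.6 leaves causality to the investigator's judgment. It is too strong to say that an abdominal reaction must be assessed against IV.
- **The window is narrow.** The Pre-Period 2 visit includes an adverse-event check and a limited examination that may cover skin and abdomen (Protocol 6.2.1.5, 6.2.2.1). The skin irritation cited in Protocol 1.3 is attributed to alkaline furosemide, whereas the study formulation is buffered to neutral pH.
- **Impact is bounded.** Adverse-event analysis is descriptive, and subject listings and photographs allow an event to be traced.
- **Counting worsening in the new period is conventional.** For systemic events that is reasonable. For a reaction at the previous treatment's site it gives the wrong attribution.

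What remains is the rule itself: applied as written to a known start date, it cannot place a late-starting SC-site reaction under SC alone, and nothing in either document breaks the tie. Traceable listings do not correct the summary table.

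**Conclusion.** The point holds as a defect in a stated classification rule. A late-starting administration-site reaction to the first treatment is counted under the second treatment or under both, and never under its own treatment alone. A local reaction that worsens after the second dose can also be counted in Period 2.

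The size is 9.5 points per event on the SC minus IV difference if counted as IV only and 4.8 if double-counted with 21 per treatment, or 11.1 and 5.6 with 18. This assumes equal denominators and no other event of the same term in that subject. The documents give no frequency of delayed reactions, so neither a total effect nor a net direction can be stated. The primary PK analysis and the injection-site pain scores, which are summarised by treatment and time point, are untouched. The rule should be corrected before the safety tables are produced, because it bears on a secondary objective and is cheap to repair.

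**What to change.** In SAP 9.3.1:

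1. Assign any adverse event located at a study-drug administration site to the treatment given at that site, whatever the period of onset or worsening. Take the site from the adverse-event record or photograph. Keep dosing sites distinct from PK blood-draw sites, since Protocol 6.2.2.6 allows venipuncture or an indwelling catheter.
2. For all other adverse events, let the onset period decide.
3. Replace the and/or causality alternatives in both periods so that each event counts under exactly one treatment.

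In Protocol 7.7.8, state that causality of an administration-site event is assessed against the treatment given at that site.

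The cost is about one sentence in each document and a site check for local events; no new visits, subjects or samples are needed. The documents specify the photograph but do not say that the adverse-event record captures the site, so that should be confirmed. The protocol sentence needs IRB approval as an amendment (Protocol 9.1.2). The SAP change can be made on its own and by itself corrects the tables.

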7.1. Definition of an Adverse Event

An Adverse Event (AE) is any untoward medical occurrence associated with the use of a Study Treatment or Study Drug (refer Section 3.1.1 for study treatment definitions) in humans, whether considered related to the Study Treatment. An adverse event (also referred to as an adverse experience) can therefore be any unfavorable and unintended sign (including an abnormal laboratory finding), symptom, or disease temporally associated with the use of a Study Treatment and does not imply any judgment about causality. An adverse event can arise with any use of the Study Treatment (e.g., off-label use, use in combination with another drug) and with any route of administration, formulation, or dose, including an overdose.

A “pre-existing” condition is one that is present prior to administration of study treatment and is reported as part of the Subject’s medical history. Pre-existing conditions should be reported as AEs only if the frequency, intensity, or character of the pre-existing condition worsens during the study.

Laboratory or functional test abnormalities generally are not considered AEs unless they are associated with clinical signs or symptoms or require medical intervention.

A laboratory abnormality (e.g., a clinically significant change detected on clinical chemistry, hematology, urinalysis) or functional test abnormality (e.g., a clinically significant change detected on ECG, pulse oximetry, or spirometry) that is independent from a known underlying medical condition and that requires medical or surgical intervention, or leads to treatment interruption or discontinuation, must be considered an AE.

All AEs judged to be clinically significant, including clinically significant laboratory results, ECG and functional test abnormalities, will be followed until resolution or return to baseline or until no further improvement is expected.

An AE **does** include any:

- Exacerbation of a pre-existing illness.
- Increase in frequency or intensity of a pre-existing episodic event or condition.
- Condition detected or diagnosed after study treatment placement and/or drug administration even though it may have been present prior to the start of the study.
- Continuous persistent disease or symptoms present at baseline that worsen following the start of the study.

An AE **does not** include a/an:

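### The Period 2 TEAE rule in SAP 9.3.1 tests absence over the washout, not the state at Period 2 dosing, so it can drop a same-or-lower-severity recurrence and does not give one answer.

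*SAP*

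**What the plan says.** SAP 9.3.1 assigns AEs to periods as follows.

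- **Period 2, first bullet.** The event must start "on or after the start of dosing in Period 2 having been absent in washout period (or) worsen in severity". The second alternative continues: "worsen in severity relative to the pre-treatment state following administration of study drug in Period 2".
- **Period 2, second bullet.** It adds "AEs that emerge during the Follow-up Phase and/or are causally related to the study treatment administered in the time preceding the Follow-up Phase".
- **Washout events.** They belong to Period 1, through "AEs that emerge during the washout period and/or are causally related to the study treatment administered in the time preceding the washout period". Protocol 7.7.8 agrees on attribution: "the causal relationship will be assessed in relation to the study treatment administered in the time preceding the washout or Follow-up period".
- **Residual class.** A paragraph about AEs before Period 1 treatment ends with "All other adverse events will be considered" pre-treatment.
- **Default.** The next paragraph classes an AE as treatment emergent when it is not possible to decide.

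SAP 2 describes "two crossover periods separated by a 3 ± 1 day washout period". SAP 9.3.1 requires TEAE summaries by treatment, both overall and for each period. SAP 9 gives the SAP precedence over the protocol.

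**The concern.** In a crossover, emergence in the second period is naturally judged against the subject's state just before the second dose. The SAP uses the washout instead. The washout is not a drug-free background here, because the SAP itself attributes washout events to the Period 1 treatment. An event already counted for one treatment can therefore become the reason for not counting its recurrence under the other.

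Example: a subject has a mild headache 20 hours after the Period 1 dose, which resolves, and a new mild headache 3 hours after the Period 2 dose. On a literal reading the second headache was not absent in washout and is not worse, so it fails the first bullet. If the first headache had come at Hour 10, while the subject was still in the research unit and before washout, the same second headache would count.

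Describing the safety and tolerability of SCP-111 is a secondary objective. Each subject receives the same active drug twice within days, so a recurrence is plausible. A dropped recurrence lowers the TEAE count of whichever treatment came second, which is SC for about half the subjects under 1:1 allocation. If washout event rates differ between IV and SC, the two treatments would be affected unequally.

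**Working it through.** The plan gives no figure to reproduce. The point is a classification rule, so it was checked as a logic table.

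**Case examined.** An event occurs and resolves in washout, and a new episode of it starts after the Period 2 dose.

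**Inputs.** There are three severity levels (Protocol 7.4) for the washout episode and three for the new one, and relatedness is grouped as related or unrelated (SAP 9.3.1). That gives 3 × 3 × 2 = 18 combinations. Of the 9 severity pairs, 3 have a more severe new episode, 3 are equal and 3 have a milder one. So 6 of 9 are no worse.

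| Reading of SAP 9.3.1 | Excluded from Period 2 |
|---|---|
| A. Absent means at no time in washout; worsening is judged against the washout episode; second bullet limited to Follow-up onset | 6 pairs × 2 = 12 of 18 |
| B. As A, but the second bullet's causal clause is taken literally and admits related events | 6 pairs × 1 = 6 of 18 |
| C. Pre-treatment state means just before the Period 2 dose, when the event had resolved, so its return is a worsening | 0 of 18 |
| D. The wording is taken as undecidable, so the conservative default applies | 0 of 18 |
| E. Each AE is its own record, so the new episode was itself absent in washout | 0 of 18 |

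These are counts of combinations, not probabilities. Under A and B the excluded episode falls to the residual sentence and would be called pre-treatment although it began after dosing. The subject would then be counted for that term only under the Period 1 treatment.

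**Effect on incidence.** The documents give no AE rates, so no expected loss can be computed. Purely as an assumption, suppose 10% of the 21 subjects have a given term in washout and 10% have it in Period 2. Under Reading A, with every recurrence no worse, the loss for that term is:

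- no overlap between the two groups: 0 subjects
- independence: 21 × 0.10 × 0.10 = 0.21 subjects
- complete overlap: 21 × 0.10 = 2.1 subjects

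The rate must be that of the same term in both windows. Overall TEAE incidence would lose less, because a subject with any other Period 2 event still counts.

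**After the fix below.** Every one of the 18 combinations starts after Period 2 dosing and was not ongoing then, so all 18 count.

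**The case against.** A reader might infer that any new post-dose episode of a washout event is always left out. The documents do not support that, because none of the readings excludes all 18 combinations.

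- Absence is one of two alternatives. A more severe new episode counts on every reading.
- The SAP does not say that absence must hold throughout the washout.
- The rule speaks of AEs with their own onset. Protocol 7.5 gives each AE an outcome, including resolved, so a second headache can be a separate AE.
- The residual sentence closes a paragraph about events before Period 1 treatment. Applying it to an event 3 hours after the Period 2 dose is the harshest reading, and the conservative default follows directly.
- The pharmacological events most likely to recur are also the ones most likely to be judged related, and the second bullet may admit those.

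All of this stands, and it reduces the point to an ambiguity that can miscount. It does not remove it:

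- Reading C makes the absence condition redundant. It also treats the change from none to mild as a rise in severity, on a scale that starts at mild. SAP 5 does define a Period 2 baseline, but for change from baseline, and 9.3.1 does not refer to it.
- The default may never be reached, because a programmer applying the literal rule gets a definite answer.
- Under Reading B, emergence depends on a causality judgement in an open-label study, and unrelated recurrences that are no worse are still lost.

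It could also be argued that the rule conflicts with the protocol by ignoring frequency, since Protocol 7.1 lists "Increase in frequency or intensity of a pre-existing episodic event or condition" as an AE. That does not hold as a contradiction: 7.1 defines what an AE is, not when it is treatment emergent.

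**Conclusion.** The concern holds as an ambiguity with a possible miscount. SAP 9.3.1 can drop from the Period 2 TEAE tables a new post-dose episode of equal or lower severity than one that resolved in washout, at least when it is judged not related. Defensible readings exclude 12, 6 or none of the 18 combinations, so the rule does not fix one derivation in advance.

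The effect on reported incidence is unknown without AE rates and may be very small in 21 subjects. AE summaries are descriptive (Protocol 8.6), all safety data remain in the subject listings (SAP 9.3), and the primary AUC analysis does not depend on the rule. A change is still worthwhile, because the tables report a secondary objective and the correction is specific and cheap.

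**What to change.** In SAP 9.3.1, define a Period 2 TEAE as either:

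- any AE with onset at or after the start of Period 2 dosing, including a new episode of an event that had resolved; or
- an event ongoing at the start of Period 2 dosing that then worsens in severity.

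Replace the condition of absence in washout with one that the event was not ongoing at the start of dosing in Period 2. Limit the pre-treatment label to AEs with onset before the first Period 1 dose. Washout events stay with the Period 1 treatment as now. Adding increased frequency as a worsening criterion is optional.

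The cost is a wording change and one derivation rule. TEAE counts may become slightly less favourable.
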